D.5.c. Design and Methodological Considerations

D.5.c.1. We chose a 12-week treatment period to ensure that patients receive adequate exposure to TOP at a dosage adequate to produce a treatment effect. We will focus the analysis on the last six weeks of treatment, by which time the TOP dosage will be 200 mg/day, a dosage at which clear separation from placebo has been seen in prior studies (5-8).

D.5.c.2. We chose the 200-mg/day dosage of TOP, which was shown by Miranda et al. (8) and by us (7) to be well tolerated and to reduce heavy drinking significantly. The 300-mg dosage, although efficacious, resulted in significantly greater dropout than placebo in a multi-center trial (6).

D.5.c.3. We chose to use the immediate-release formulation of TOP, administered twice daily, rather than Trokendi XR™ or Quedxy XR™, which are new, once-daily formulations of TOP. We chose the immediate-release formulation of TOP because it is generic and inexpensive, and its use to treat AUD in the VAHS is growing rapidly (9). If TOP is efficacious in this study, it would be of potential interest to compare the efficacy and tolerability of the immediate-release and the once-daily TOP formulations, which is beyond the scope of the present proposal.

D.5.c.4. We will enroll actively drinking individuals with a goal of reduced drinking or abstinence because studies using these goals showed robust effects of TOP in reducing heavy drinking. Although we will include patients with a DSM-5 diagnosis of AUD, we will require that patients have a weekly average of ≥ 2 heavy drinking days during the month before screening, consistent with the inclusion criteria for our TOP study in heavy drinkers (7). These criteria will enhance the study's external validity and applicability to the current diagnostic system while ensuring that we can detect a treatment effect on heavy drinking days.

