The two medication groups will be compared on weekly number of heavy drinking days and weekly number of abstinent days using mixed effects models for count responses, fitted using PROC GLIMMIX in SAS and the HGLM module of the HLM7 program (57). Estimates of effects over the final six weeks from the models, with associated standard errors and confidence intervals, will be used to test the primary hypotheses, i.e., that TOP treatment will reduce heavy drinking days and increase abstinent days more than placebo during the final six weeks of treatment. The models will include covariates for linear and quadratic time trends, as appropriate for model fit. The random effects will include a random intercept and, if necessary, residual autocorrelations, random slopes, or other specifications will be used. Although the primary contrasts will concentrate on the final six weeks, these models utilize all available data from all patients, so the analyses follow the intent-to-treat principle.

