D.7.b. To explore the moderating effects of variation at *GRIK1* and other glutamate system genes on the efficacy of TOP 200 mg/day in reducing the frequency of heavy drinking and increasing the frequency of abstinent days (Specific Aim 2). Specific Aim 2 will be addressed by including a binary indicator of the SNPs identified as being associated to sustained heavy drinking through the MVP beta test project in the models described above for testing Specific Aims 1. These models will include the main effect of the SNP indicator and its interaction with medication group and time. Analyses will be conducted and results described as above. To identify candidate variants to test in the pharmacogenetic analyses, we will select SNPs in *GRIK1* and *GRIK2* (the genes that encode the GluK1 and GluK2 kainate subunits, on which TOP's effects are most potent and selective (39), using data from the MVP project, or alternatively from the GWAS that we completed on 3,318 AAs (11). We will select the 10 SNPs in these genes that yield the smallest p-values (ideally, but not necessarily, the p-values for these SNPs will be smaller than the p-value that is typically used to determine genomewide significance: $p < 5.0 \times 10^{-8}$). We will test for moderating effects by starting with the most significant SNP and continuing until one shows significance, with the value of α adjusted each time to reflect the number of comparisons (such that the tenth SNP would be tested using $\alpha = 0.005$). We will also construct a gene-based analysis, considering common variation mapped to genes that are implicated as being associated to sustained heavy drinking in the MVP sample or alcohol dependence in our sample (11). We will use the approach developed by Lin and et al. (58), where the interaction effect between an environment (treatment in our case) and all the SNPs within a gene can be considered in a unified framework. Analyses will be conducted and results described, as above. In particular, separate estimates and confidence intervals will be reported for the TOP effects in the two levels of each binary genotypic indicator. The outcomes for Aim 2 are exploratory.

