D.7.c. To examine the persistence of effects of TOP treatment on the number of heavy drinking and abstinent days during a six-month post-treatment follow-up period (Specific Aim 3). We will use linear mixed models to examine medication group differences in percent heavy drinking days, percent days abstinent, SIP, GGTP, and %dCDT across the treatment and post-treatment periods. The 12-week treatment period, along with the 3-month and 6-month follow-up periods will be included in the analysis to determine whether the change in outcomes from treatment to follow-up differ by medication group. The models will include study period (treatment period, 3-month follow-up, 6-month follow-up), treatment group (TOP, placebo) and the interaction between these two factors to test for differences between study periods, treatment groups, and the change in the difference between groups across study periods. Baseline (pretreatment) values for each outcome will be included as covariates in modeling the respective outcome. The outcomes for Aim 3 are considered exploratory. We will also explore the persistence of TOP effects using the primary SNP identified in Aim 2. That is, we will conduct a pharmacogenetic analysis of the persistent effects of TOP, similar to our analysis of heavy drinking in EAs, where rs2832407*C homozygotes treated with TOP had robust reductions in heavy drinking during the six-month post-treatment period (10).

D.7.d. Dropout and Missing Data: We will base the primary relative efficacy comparisons in the trial on mixed effects models utilizing all data provided by participants. In our completed TOP trial, we saw limited dropout (8% to the start of the final six weeks, and 4% thereafter). We will assess the sensitivity of our assumption that missing data are ignorable by running models that address missingness in different ways. For mixed effects models, pattern mixture models test for differences in regression estimates across patterns of missing data, and shared parameter models allow for correlated random effects for the primary responses and the week-to-week binary indicators of missing/complete data (57). Semi-parametric regression models use inverse probability weighting to extend the validity of GEE models, and provide a different type of sensitivity analysis for the mixed effects models (59). All of these modeling approaches require certain model assumptions, so we will compare the results of the analyses over a range of such assumptions.

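### For the two drinking-diary outcomes, Aim 3 measures post-treatment loss against a 12-week mean that includes titration; if the effect builds gradually, the interaction understates loss from the weeks 7–12 effect (minor, exploratory aim)

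*Combined protocol and SAP*

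**What the plan says.** For Aim 3, section D.7.c specifies linear mixed models with a three-level study period (treatment, 3-month follow-up, 6-month follow-up), treatment group and their interaction, adjusted for baseline. On the treatment level it says: "The 12-week treatment period, along with the 3-month and 6-month follow-up periods will be included in the analysis". The interaction is there to test "the change in the difference between groups across study periods". No week term within treatment and no restriction to later weeks is named. The section adds: "The outcomes for Aim 3 are considered exploratory".

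Aim 1 is handled differently. Section D.5.c.1 explains: "We will focus the analysis on the last six weeks of treatment, by which time the TOP dosage will be 200 mg/day". Section D.7.a keeps all weeks in the model but restricts the test: "Although the primary contrasts will concentrate on the final six weeks, these models utilize all available data from all patients". It also models time within treatment: "The models will include covariates for linear and quadratic time trends".

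Table 1 gives daily doses of 25, 50, 75, 100 and 150 mg in weeks 1–5 and 200 mg in weeks 6–12. Section D.7.g names effect-size estimates for persistent effects, to inform later studies, as what Aim 3 should yield.

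**The concern.** The plan uses two different definitions of the on-treatment effect for the same two diary outcomes. Aim 1 defines it over weeks 7–12, when the dose is 200 mg/day. Aim 3 averages over all 12 weeks, five of them below that dose. Whether the Aim 3 model is fitted to weekly rows or to one summary per period, its treatment level is a 12-week mean.

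If the effect grows over the first weeks, that mean is smaller than the effect Aim 1 will report. The change from treatment to follow-up then mixes early build-up with later loss, and the loss looks smaller than it is. Section A hypothesizes persistence in a responsive subgroup, so the error would lean towards the hypothesis. What is at stake is one exploratory estimate that later trials might use; the Aim 1 result is not involved.

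The documents make build-up plausible without settling it. Section B.1.b reports group-by-week interactions in the sponsor's 200-mg trial for heavy drinking days (p<0.0001) and abstinent days (p=0.013), and a 300-mg trial that separated from placebo after the first month. It also reports a 61-person trial with significantly less heavy drinking already during titration. None of these gives weekly effect sizes.

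**Working it through.** The plan states no effect, power or sample-size figure for Aim 3, so there is none to reproduce.

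**Inputs from the documents**
- Doses by week: Table 1.
- D = 0.52–0.62 for heavy drinking days in weeks 7–12 of the prior trial: D.7.f.
- Within-subject correlation about 0.6: D.7.f.
- 160 patients in two arms (D.1), 80 per group. This agrees with D.7.f, where 80 × 0.92 = 73.6, stated as 74.
- Six-month data rate of 85.5% in the prior trial (B.1.b): 80 × 0.855 = 68 per group.

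**Assumptions**
- D is in SD units of the weekly outcome and carries over to the percent scale of Aim 3.
- The onset shape, expressed as f.
- The correlation between treatment and follow-up weeks, c.

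**Size of the shortfall.** With effect fD in weeks 1–6 and D in weeks 7–12, the 12-week effect is D(1+f)/2. The shortfall against D is D − D(1+f)/2 = D(1−f)/2. If follow-up loses a share L of D, the apparent loss relative to the 12-week effect is 1 − (1−L)/((1+f)/2).

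If the effect follows dose, the mean dose in weeks 1–6 is (25+50+75+100+150+200)/6 = 100 mg. This is half of 200 mg, so f = 0.5. For a linear rise over weeks 1–6, f = (1+2+3+4+5+6)/36 = 0.583.

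| Onset | f | Shortfall, D = 0.52 to 0.62 | True 25% loss shows as | True 50% loss shows as |
|---|---|---|---|---|
| Immediate | 1 | 0 | 25% | 50% |
| Mostly early | 0.75 | 0.065 to 0.078 | 14% | 43% |
| Linear over weeks 1–6 | 0.583 | 0.108 to 0.129 | 5% | 37% |
| Follows dose | 0.5 | 0.13 to 0.155 | 0% | 33% |

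In the last row, full retention of D would show as an apparent gain of 0.25D.

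**Cost in precision.** The variance of a k-week mean is V(k) = (1+(k−1)×0.6)/k, so V(6) = 0.667 and V(12) = 0.633. For a 13-week follow-up period, V(13) = 0.631. The standard error of the contrast is sqrt((2/68) × (V(k)+V(13)−2c)). A baseline main effect cancels from this within-subject contrast when data are complete.

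| c (assumed) | SE, weeks 7–12 | SE, 12 weeks | Increase |
|---|---|---|---|
| 0.32 | 0.139 | 0.136 | 2.6% |
| 0.45 | 0.108 | 0.1035 | 4.5% |
| 0.50 | 0.0935 | 0.0881 | 6% |
| 0.60 | 0.0535 | 0.0434 | 23% |

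If instead the 6-week and 12-week means correlate equally with the follow-up mean (0.5–0.7), the increase is about 1%.

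**Break-even, heavy drinking days only.** The two variances differ by (2/68) × (0.667−0.633) = 0.00098 whatever c is, and its square root is 0.0313. Setting D(1−f)/2 = 0.0313 gives f = 1 − 2×0.0313/D, which is 0.88 at D = 0.52 and 0.90 at D = 0.62. Below that f, the weeks 7–12 reference has the lower mean squared error for loss from the full-dose effect. Above it, the 12-week reference is slightly better.

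**The case against.** The strongest reply is that the 12-week mean answers a different question and is not an error. D.7.c asks how the group difference changes from treatment to follow-up, and nothing in the plan says that Aim 3 must use the Aim 1 window. A 12-week period also matches the length of the 3-month follow-up periods. This stands, and it is why the planned contrast should be kept.

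Next, the 3- and 6-month group differences show directly whether an effect persists, and they do not use the treatment level at all. This stands too. A reader might infer that Aim 3 as planned cannot answer the persistence question. The documents do not support that; only the change from treatment to follow-up depends on the reference.

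Third, the size depends on quantities the documents do not give. Onset is unknown, and the range includes no shortfall. D is stated for heavy drinking days only. With an assumed D of 0.30, break-even falls to f = 1 − 0.0626/0.30 = 0.79, so the figures above should not be carried over to abstinent days. The formula applies to both outcomes; the numbers do not.

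Last, Aim 1 already reports a weeks 7–12 effect that can be set beside the follow-up differences. This helps only in part, because Aim 1 uses count models and Aim 3 uses percent-day linear models.

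**Conclusion.** This is a minor point and a cheap improvement to an exploratory analysis. For the two Timeline Follow-back outcomes, the planned interaction understates loss from the Aim 1 effect if the effect builds during titration. The sponsor's own group-by-week interactions make that plausible, while the 61-person trial suggests at least some early effect. For heavy drinking days the shortfall runs from zero (immediate onset) to 0.13–0.16 SD (effect follows dose). This rests on D = 0.52–0.62 carrying over to the Aim 3 scale. For abstinent days the direction is the same under build-up, but the size cannot be given.

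Two wider readings go beyond the documents. A reader might infer that the other Aim 3 outcomes are clear of the problem because they are not weekly averages. For %dCDT that is not shown: it is repeated at the midpoint and end of treatment (D.5.a), and D.7.c does not say which values enter the treatment level. GGTP is named at baseline (D.3.a), but Table 2 lists no later draw. This point makes no claim about either. A reader might also take the lack of stated confidence intervals in D.7.c as part of the defect. That is only missing reporting detail, and D.7.g already promises effect-size estimates.

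**What to change.** In D.7.c, for percent heavy drinking days and percent days abstinent, add a treatment-to-follow-up contrast that takes weeks 7–12, the Aim 1 window, as the treatment level. Report it beside the planned 12-week contrast. State in advance that loss from the full-dose effect will be read from the weeks 7–12 version, and that the 12-week version describes change from the treatment period as a whole.

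This changes wording only. Timeline Follow-back data are collected at each visit for the time since the last one (Table 2, note a), so every treatment week is already covered. The costs are a standard error about 1% to 23% larger, depending on a cross-period correlation that the documents do not give, a treatment window shorter than the follow-up periods, and a second version of an exploratory contrast to report.

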Specific Aim 1. To test the efficacy of topiramate (TOP) 200 mg/day in reducing the frequency of heavy drinking and increasing abstinent days in African-American (AA) patients with alcohol use disorder (AUD). We hypothesize that, as in EAs, AA Veterans receiving TOP will report fewer heavy drinking days (HDDs) and more abstinent days than those receiving placebo.

Specific Aim 2. To explore the moderating effect of variation in the *GRIK1* and *GRIK2* genes on TOP’s efficacy in reducing heavy drinking and increasing abstinent days. We will explore the moderating effects of single nucleotide polymorphisms (SNPs) in *GRIK1* and *GRIK2*, which encode kainate subunits. Topiramate’s effects are most potent and selective for kainate receptors containing these subunits. We will select SNPs for testing based on association analyses for sustained heavy drinking that are being conducted in a beta test project of the MVP ([name], PI at CMCVAMC) or from a GWAS that we completed in a sample of 3,318 AAs (11).

Specific Aim 3. To examine the persistence of TOP treatment effects during a six-month post-treatment follow-up period. We hypothesize that, in a pharmacogenetically responsive subgroup, TOP’s effects on heavy drinking and abstinent days will persist during the follow-up period.

B. BACKGROUND AND SIGNIFICANCE

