Open-label trials of TOP conducted in Spain (29) and in Greece (30) also provided evidence of the utility of TOP in individuals of European descent. However, a placebo-controlled study conducted in Thailand failed to show a significant advantage of TOP in reducing drinking in that population (31). The interpretation of the findings from that study is limited by the low rate of study completion (53% in the TOP group and 47% in the placebo group) resulting in a large amount of missing data. Further, there was no evaluation of adherence to the prescribed regimen. A meta-analysis of 7 randomized controlled trials (a total of 1,125 participants) compared topiramate to placebo for treating AUD(4). The largest effect for topiramate was found on the following outcomes: abstinence ($g = 0.468$, $p < 0.01$), heavy drinking ($g = 0.406$, $p < 0.01$), the liver enzyme GGT ($g = 0.324$, $p = 0.02$), and craving for alcohol ($g = 0.312$, $p = 0.07$). The authors concluded that the efficacy was greater magnitude than that of either naltrexone or acamprosate. However, despite a growing literature on the use of TOP for treating AUD, there are no published studies that have enrolled a substantial number of African-ancestry patients, so that our knowledge of the potential utility of TOP for treating AUD in AAs is non-existent.

We completed a 12-week, placebo-controlled trial of the efficacy of TOP 200 mg/day. The dosage in that study was chosen to be more tolerable than the 300-mg/day dosage used in most of the prior studies. The study enrolled 138 heavy drinkers [62.3% male, 88.4% European American (EA)] whose goal was to reduce their drinking (7). Patients were randomly assigned to receive 12 weeks of treatment with TOP (N=67, 48.6%) or matching placebo (N=71, 51.4%), together with medical management. During the 90-day pre-treatment period, patients in both groups were abstinent ~1 day/wk and drank heavily (men: ≥ 5 standard drinks; women: ≥ 4 standard drinks) on ~5 days/week. Fifty-six TOP patients (83.6%) and 61 placebo patients (85.9%) completed the 12-week treatment period ($p=0.70$). There was a main effect of medication group ($p<0.001$) and

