an interaction of medication group with treatment week ($p<0.0001$), such that TOP patients had fewer heavy drinking days and decreased the number of heavy drinking days/week more rapidly than placebo patients (see Fig. 1 below). During week 12, the odds that the TOP group would have at least one heavy drinking day was 0.188 (95%CI=0.137-0.595) that of the placebo group ($p<0.001$). There was also a main effect of medication group on abstinent days ($p=0.032$) and an interaction with treatment week ($p=0.013$), such that TOP patients had more abstinent days and increased the number of abstinent days/week more rapidly than the placebo group. During week 12, the odds of an abstinent day in the TOP group was 2.57 (95%CI=1.13-5.84) times that of the placebo group. These findings were accompanied by significantly greater reductions in gamma-glutamyltranspeptidase (GGTP), a liver enzyme that is elevated by heavy drinking, and scores on the Short Index of Problems (SIP), a measure of alcohol-related problems, in TOP patients compared with those receiving placebo (32). These findings help to validate the self-reported drinking reductions seen in the TOP group.

[figure not shown]

Figure 1. Heavy drinking days per week during treatment. A. All subjects (n=138); B. EA rs2832407*C-allele homozygotes (n=51); C. EA rs2832407*A-allele carriers (n=71).

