D.7. Data Analyses: The study will use the web-based direct entry data management system of the Penn Center for Studies of Addiction, with data stored on secure servers at the CMCVAMC. This arrangement has been approved and is described in a Memorandum of Understanding between the CMCVAMC and the Perelman School of Medicine at Penn. Interview data and self-report data are entered directly onto computers by research staff and/or subjects under supervision by staff. A range of checks for the validity of responses (including field validation to ensure that no out-of-range or otherwise invalid responses are accepted), and form validation (to ensure that logically impossible responses to different questions are not accepted) are built into this entry process. After entry, the research staff performs a brief review to ensure that the form has been completed. On completion of this review, the technician transmits the data (in 128-bit encrypted form) over the Internet to the DMU data servers. After a series of online reviews, the data are archived on the servers without protected health information. Audit logs record any modification to the original entry. Various levels of password protection will allow access to the data by members of the research team.

An important initial consideration will be to identify baseline differences between groups that may have occurred despite the use of block randomization. Prior to analysis, the distribution of outcome data will also be examined to determine the need for transformation and whether parametric analytic methods can be used.

D.7.a. To examine the effects of TOP treatment on the number of heavy drinking and abstinent days during the final six weeks of treatment (Specific Aim 1). The two primary outcomes, which will be measured using the TLFB, are the frequency of heavy drinking days (≥ 5 standard drinks in a day for men and ≥ 4 in a day for women), a sensitive, clinically relevant measure in alcohol treatment trials, and the frequency of abstinent days (56). An attempt will be made to evaluate outcomes for all patients irrespective of whether they continue to receive treatment, so that the analysis of all outcomes will be based on all of the data available for all randomized patients. Secondary outcomes for Aim 1 will include the severity of alcohol-related problems (i.e., SIP score) and %dCDT, which will be analyzed using models similar to those described below for the primary outcomes.

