D.7.e. Adherence: To assess the sensitivity of the results of the analyses described above to non-adherence, the models described above for our primary and secondary outcomes will be extended using instrumental variable approaches. Under some assumptions, these analyses will yield estimates of the intervention effects that would have been seen in a study with full adherence. To analyze data using a single overall measure of adherence (e.g., 80% of assigned medication taken over the 12 weeks of treatment), we will use the methods of Nagelkerke et al. (60). We will also examine longitudinal extensions of these methods, looking at weekly adherence to medications as a time varying measure (61).

D.7.f. Adequacy of Sample Size for Specific Aim 1: The analyses described above make use of all data provided by all patients to estimate models from which contrasts restricted to the final six weeks will test the TOP effect on days of heavy drinking and abstinent days (Specific Aim 1). Power for the contrasts will be determined by the patterns of outcomes in the final six weeks, so power estimates are based on weeks 7

through 12 as a 6-week trial, with adjustments for loss to attrition between baseline and week 6. Based on our prior study (7) we anticipate 92% retention through the first six weeks for each group, yielding 74 available per group at the end of week 6, an additional 4% loss due to dropout across the final six weeks, and a within-subject correlation of about 0.6. The methods of Hedeker et al show that we will have 80% power for a TOP main effect size of $d=0.40$, 0.43 , and 0.46 , for within-subject correlations of 0.5 , 0.6 , and 0.7 , respectively, at a corrected alpha level of 0.025 (62). In [name] et al, the effect sizes for heavy drinking days in weeks 7 through 12 varied between $d=0.52$ and $d=0.62$, so the sample size should be adequate to detect similar effects in the current study (7).

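### The corrected alpha of 0.025 reads as a Bonferroni split of the two primary outcomes; Holm would give more power on the second outcome at the same 5% familywise error

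*Combined protocol and SAP*

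**What the plan says.** Section D.7.a of the combined protocol and SAP sets out the Aim 1 analysis: "The two primary outcomes, which will be measured using the TLFB, are the frequency of heavy drinking days", with the frequency of abstinent days as the second. Specific Aim 1 makes both part of the hypothesis: "AA Veterans receiving TOP will report fewer heavy drinking days (HDDs) and more abstinent days than those receiving placebo". The treatment contrasts over the final six weeks, "with associated standard errors and confidence intervals, will be used to test the primary hypotheses".

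The only alpha given for Aim 1 is in the sample-size section, D.7.f. It claims 80% power for d = 0.40, 0.43 and 0.46 at within-subject correlations of 0.5, 0.6 and 0.7, "at a corrected alpha level of 0.025". D.7.a does not repeat that level, and gives no sidedness, familywise level or named procedure. By contrast, D.7.b does spell out a stepwise alpha adjustment for the exploratory SNP tests.

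D.7.f cites an anticipated effect only for heavy drinking days (d = 0.52 to 0.62, from the completed trial). It gives none for abstinent days.

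**The concern.** Two primary outcomes and a corrected level of 0.025 point to a Bonferroni split of 0.05. That controls familywise error, but a fixed 0.025 for both outcomes gives up power on one outcome after the other has already been shown positive. Holm recovers that power at no cost in error control.

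The two rules differ only when one outcome has p below 0.025 and the other has p between 0.025 and 0.05. The completed trial described in section B.1.b had that pattern in its medication main effects: p<0.001 for heavy drinking days and p=0.032 for abstinent days. With 0.025 for each, abstinent days would have been negative; under Holm, positive. What is at stake is therefore the second claim of Aim 1, on the outcome that had the weaker evidence in that trial.

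**Working it through.** **Inputs from the plan.** 160 patients in two arms, so 80 per arm (inferred from 0.92 × 80 = 73.6, given as 74). A further 4% loss leaves 74 × 0.96 ≈ 71 per arm. Six weekly measures (weeks 7–12), with within-subject correlation ρ about 0.6.

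**Assumed, not in the plan.** The correlation between the two test statistics (0.5–0.7, varied more widely below) and the effect on abstinent days.

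**Step 1: reproduce the stated power.** For the mean of six weekly measures under compound symmetry, SE = √[(2/71)(1 + 5ρ)/6], and power ≈ Φ(d/SE − z). The critical value z is 2.241 for two-sided 0.025 and 1.960 for one-sided 0.025.

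| ρ | d | SE | d/SE | two-sided 0.025 | one-sided 0.025 |
|---|---|---|---|---|---|
| 0.5 | 0.40 | 0.1282 | 3.120 | 81.0% | 87.7% |
| 0.6 | 0.43 | 0.1370 | 3.138 | 81.5% | 88.1% |
| 0.7 | 0.46 | 0.1454 | 3.165 | 82.2% | 88.6% |

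With 70 per arm (12% taken off 80), the two-sided figures are 80.4, 80.9 and 81.6%. The stated 80% fits two-sided 0.025 and not one-sided. Since 2 × 0.025 = 0.05, the natural reading is a Bonferroni split of a two-sided 0.05.

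**Step 2: compare the rules.** The two z-statistics are taken as bivariate normal with means d/SE (SE = 0.1370, ρ = 0.6).
- Bonferroni: an outcome is positive if its p < 0.025.
- Holm: an outcome is positive if its p < 0.025, or if its p < 0.05 while the other p < 0.025.

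So Holm power for outcome 2 = P(p₂ < 0.025) + P(p₁ < 0.025 and 0.025 ≤ p₂ < 0.05).

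| Heavy drinking d | Abstinent days d | Power examined | Bonferroni | Holm |
|---|---|---|---|---|
| 0.43 | 0.43 | each outcome | 81.5% | 85–86% |
| 0.43 | 0.43 | both outcomes | 71–73% | 80–81% |
| 0.52 | 0.52 | each outcome | 94.0% | about 96% |
| 0.62 | 0.62 | each outcome | 98.9% | 99.4% |
| 0.52–0.62 | 0.30 | abstinent days | 48% | 59% |
| 0.52–0.62 | 0.35 | abstinent days | 62% | 72% |
| 0.52–0.62 | 0.468 | abstinent days | 88% | 92–93% |

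The rules give different results in 8–9% of trials with both effects at 0.43, in 1–4% with both at 0.52–0.62, and in 5–11% in the last three rows. The chance of at least one positive outcome is the same under both rules (90–92% with both at 0.43). Widening the outcome correlation to 0.3–0.8 with both at 0.43, power for both outcomes goes from 69–75% to 78–82%.

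**Step 3: source of the abstinent-day effects.**
- d = 0.30 is back-calculated from p = 0.032 with 67 and 71 patients. Here z = 2.144 and SE = √[(1/67 + 1/71)(1 + (m − 1)0.6)/m], which is 0.136 for m = 12 weeks and 0.139 for m = 6, giving d = 0.29–0.30 (0.27–0.32 for ρ = 0.5–0.7). It comes from a whole-treatment effect that includes the titration weeks, so it is probably low.
- d = 0.35 is simply assumed.
- d = 0.468 is the meta-analysis g for abstinence in B.1.b, taken as d.

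**Step 4: familywise error under Holm.** With both effects null it is 4.65% at outcome correlation 0.5 and 4.3% at 0.7. With one null and the other at d = 0.52–0.62 it is 4.4–4.9%. The 5% bound holds for any dependence between the outcomes.

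**The case against.** The strongest reply is that the criticised rule is not written down. D.7.f uses 0.025 only for a power statement, and a trial planning to use Holm would also power at 0.025; D.7.a names no rule. This is true, and the Bonferroni reading is an inference. But 0.025 is the only level the plan gives for Aim 1, and a reader would apply it to each outcome.

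Second, the gain is small where the plan supplies an effect: about 2 points or less per outcome if both lie at d = 0.52–0.62. The larger gains depend on an abstinent-day effect that the plan does not give, and the 11-point gain uses a value that is probably low. That stands as a limit on the size of the gain, not on its direction.

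Third, the completed trial is a weak illustration. Its p = 0.032 is a whole-treatment main effect, not a final-six-week contrast, and it came with a significant treatment-by-week interaction. The week-12 odds ratio for abstinence, 2.57 (1.13–5.84), gives ln 2.57 = 0.944, SE = (ln 5.84 − ln 1.13)/3.92 = 0.419, z = 2.25 and p of about 0.024, which passes under both rules. This also stands. Both p-values lie close to 0.025, so neither shows what this trial will find.

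Fourth, D.7.a relies on confidence intervals. Bonferroni has matching 97.5% intervals; Holm has no equally simple ones. An outcome with p between 0.025 and 0.05 could be declared positive while its 97.5% interval includes no effect. This is a real cost, and a sponsor could reasonably weigh it.

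**Conclusion.** The point holds as an inexpensive improvement. The plan's apparent rule is valid and its stated power reproduces, so nothing in D.7.f is wrong. Holm is never worse on rejections and keeps familywise error at or below 5%; that part needs no assumption about the data.

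The size of the gain does depend on assumptions. It runs from about half a point per outcome (both effects at d = 0.62) to about 11 points for abstinent days (assumed d = 0.30, with heavy drinking at 0.52–0.62). At the plan's own detectable effect of 0.43 for both outcomes it is about 4 points per outcome and 8–9 points for establishing both. These figures rest on 71 per arm, ρ = 0.6, an assumed outcome correlation of 0.5–0.7 and a normal approximation. The benefit is confined to the second outcome.

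**What to change.** In D.7.a, state that each primary outcome is a separate claim and that the two are tested by Holm at a two-sided familywise 0.05: the smaller p-value against 0.025 and, if that is rejected, the larger against 0.05. Keep 0.025 in D.7.f as the planning level. Say in the same place how intervals will be reported, for example 97.5% intervals as description with the decision resting on the Holm p-values, so that a borderline second outcome is not read two ways.

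Holm fits separate claims, which is what a corrected alpha implies. If success instead requires both outcomes to be positive, no split is needed and each is tested at 0.05; the chance that both are positive at d = 0.43 is then 80–82%. The plan should say which it intends before unblinding.

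The cost is one or two sentences in D.7.a, with no change to sample size, data collection or the D.7.f calculation. The drawback is the loss of simple matching intervals.
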